### 9.5.1.2 MRI

Descriptive statistics on number of new / newly enlarging T2 lesions, T2 lesion total volume, T1 black hole volume and brain volume (atrophy) for change from previous scan and change from FDF baseline will be presented by time for appropriate subgroups of patients. Model based estimates will also be provided for the following endpoints:

**New / newly enlarging T2 lesions:** the annualized rate of new/newly enlarging T2 lesions will be estimated based on a negative binomial regression model with log-link. The number of new / newly enlarging T2 lesions relative to FDF baseline will be used as the response variable, and the natural log of the time (in years) of the MRI-assessment from the baseline/screening scan will serve as the offset variable to adjust for the various lengths of follow-up times between patients. The model will include treatment and baseline volume of T2 lesions as continuous covariates.

**Brain volume:** Percent brain volume change from baseline will be estimated based on a mixed effects model with repeated measures and auto-regressive within-subject covariance structure of first order will be used with visit, treatment, core baseline normalized brain volume, number of Gd-enhancing lesions at FDF baseline, and T2 lesion volume at FDF baseline as fixed effects, and individual patient as a random effect. Kenward and Rogers' adjustment for the degrees of freedom will be applied. Annualized rate of brain atrophy (ARBA) will also be estimated based on the same mixed effects model.

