 - Baseline will refer to the last value prior to the intake of the first dose of fingolimod. (Measurements labeled as "pre-dose" assessments will not be used as baseline values if the actual time variable suggests that the value has been obtained after the first dose of study medication: exceptions are body weight and temperature for which Day 1 records can be used as baseline irrespective of the actual time on day 1).
 - Multiple results per patient within a visit window will be averaged for summary statistics by considering both scheduled and unscheduled visits..
 - This visit windowing approach will only be used for summary statistics. (All individual assessments including unscheduled visits will be used to analyze notable and abnormal values, in shift tables and on listings.)
 - ** Week 2 for laboratory values will include day 1 post-baseline as the start day.

Table 2 Visit-windows for efficacy data (non-EDSS) domains

Visit	Start day (time)	Target Day (time)	End day (time)
Month 3	1	91	136
Month 6	137	182	273
Month 12	274	365	547
Month 24	548	730	912
Year 3 (M36)	913	1095	1278
Year 4 (M48)	1279	1461	1643
Year 5 M(60)	1644	1826	2008
Year 6 (M72)	2009	2191	2373
Year 7 (M84)	2374	2556	2739
Year8 (M96)	2740	2922	3104
Year 9	3105	3287	3469
Year 10	3470	3652	3834
Year 11	3835	4017	4200

...		every 12 months	
Month X (row i)	$S_i = \text{Integerpart}((D_i + D_{i-1}) / 2) + 1$	$D_i = \text{Integerpart}(X * 365.25 / 12)$	$E_i = \text{Integerpart}((D_{i+1} + D_i) / 2)$
...	...	Every 12 months	...
Month X (last row)	S_{last}	D_{last}	$E_{\text{last}} = D_{\text{last}} + (D_{\text{last}} - S_{\text{last}})$

- Day 1 is defined as the first dose day of fingolimod among all studies.
 - Baseline will refer to the last MRI value prior to Day 1.
 - For MRI: Visits 777 and 779 (study drug discontinuation assessments: the last scheduled scan is the reference scan), will be included in the visit windowing approach. However, 777 will only be used in a visit window if no other scheduled visit is available in the same window, if another scheduled visit is present, then the scheduled visit will take priority over 777.
 - If multiple assessments are available within a visit window, the record closest to the target day will be selected (if more than one assessment is at the same distance to the target day, the later one will be used for summary statistics (after unscheduled visits are excluded)).

Table 3 Visit-windows for EDSS efficacy data

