8.2.1 Annualized rates of new-/newly enlarging T2 lesions

Annualized rate of new/newly enlarging T2 lesions is defined as the *number of new or newly enlarging T2 lesions* experienced during a specific period of time adjusted to a one-year period. The group level annualized rate of new/newly enlarging T2 lesions will be calculated as follows: (total number of new/newly enlarging T2 lesions) / (total number of days in the study for all patients for that specific period of time) x 365.25. The number of days in study will be calculated based on MRI scan date and first dose date of fingolimod. The annualized rate will be provided from first dose of fingolimod.

In addition to a group level annualized rate estimate, another annualized rate estimate and corresponding two-sided 95% confidence interval will be presented from a negative binomial (NB) regression model adjusted for total volume of T2 lesions at first dose of fingolimod baseline. Log (time in study) will be the offset variable.

These annualized rate summaries will be presented by cumulative yearly intervals: Month 0 to Month 3, Month 0 to Month 6, Month 0 to Month 12, Month 0 to Month 24, etc.

In general the number of new/newly enlarging T2 lesions is provided by the reading center. It is obtained by comparing two scans (e.g. the baseline scan to the Month 24 scan). If an assessment is provided by the reading center, then this should be used. Derived parameters should only be used when no assessment from the reading center is available. It is of note that any such derived number is an approximation. When an assessment is not provided by the reading center (i.e. 2399 results relative to FDF), derivation rules regarding number of new/newly enlarging T2 lesions relative to FDF baseline should be followed as below:

- Patients who were randomized to fingolimod in core: new/newly enlarging T2 lesions relative to FDF baseline = new/newly enlarging T2 lesions relative to core baseline.
- Patients who were randomized to another treatment (placebo or interferon) than fingolimod in core and switched to fingolimod in extension:
 - If the record of extension FDD was available in the extension database, new/newly enlarging T2 lesions relative to FDF baseline = new/newly enlarging T2 lesions relative to extension FDD.
 - If no records relative to extension FDD were available, new/newly enlarging T2 lesions relative to FDF baseline = max(result relative to FDD – end of core result relative to FDD, 0).

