8.2.4 Annualized rate of brain volume change (ARBA)

The annualized rate of brain volume change is an “averaged annual percentage change” in brain volume. The logic of interest rates applies. The formula for ARBA is as below:

$$ARBA = [(SIENA/100+1) ^ (365.25/\#days)-1]*100$$

$$SIENA=(Vk/V0-1)*100$$

$$k=days/365.25$$

where V0 is the brain volume at time 0, and Vk is the brain volume at time k (where k is the time in years).

The annualized rate of brain volume change relative to FDF baseline will be calculated from the SIENA estimate of the percentage brain volume change relative to FDF baseline and the number of days in study relative to FDF. For the calculation of k and V0, below rules should be followed:

- Patients who were randomized to fingolimod: k = MRI date – first dose date +1; V0 = brain volume at FDD
- Patients who were randomized to a treatment (placebo or interferon) other than fingolimod in core and switched to fingolimod in extension control treatment: k = MRI date – first dose date of extension +1; V0 = brain volume at extension FDD (if there is record), or at the end of core (if there is no record at extension FDD) .

Descriptive statistics on ARBA will be presented by visit. Additionally, a mixed effects model with repeated measures will be used with visit, normalized brain volume at core baseline, T2 lesion volume at first dose of fingolimod baseline and Gd-T1 lesion count at first dose of fingolimod baseline as fixed effects and individual patient as a random effect. Kenward and Rogers’ adjustment for the degrees of freedom will be applied. Based on this model, least square mean, standard error, and a two-sided 95% CI will be displayed for each group.

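### SAP 8.2.1 and 8.2.4 measure MRI change from the baseline scan but time from first dose, which overstates annualized T2 and atrophy rates, mainly at early time points

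*SAP*

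**What the plan says.** **T2 lesions, SAP Part I 8.2.1.** The lesion number is a comparison of scans: "It is obtained by comparing two scans (e.g. the baseline scan to the Month 24 scan". The time is not scan to scan: "The number of days in study will be calculated based on MRI scan date and first dose date of fingolimod". That time divides the crude group-level rate and also enters the model: "Log (time in study) will be the offset variable". Rates are tabulated for cumulative intervals starting with Month 0 to Month 3.

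**Where the baseline scan lies, SAP Part I 2.3.4, notes to Table 2.** "Baseline will refer to the last MRI value prior to Day 1". It therefore precedes the first dose of fingolimod (FDF). No maximum gap is given.

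**T2 lesions, protocol 9.5.1.2.** The model's response is the lesion count since the FDF baseline scan. Its offset starts at a scan as well: "the natural log of the time (in years) of the MRI-assessment from the baseline/screening scan will serve as the offset variable". Here count and time cover the same interval.

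**Brain volume, SAP Part I 8.2.4.** ARBA is computed from the "SIENA estimate of the percentage brain volume change relative to FDF baseline and the number of days in study relative to FDF". For patients randomized to fingolimod, the time is the MRI date minus the first dose date plus 1. For patients who switched to fingolimod in the extension and have no record at the extension's first dose, the reference volume is the end-of-core scan, yet time still runs from the first extension dose. The protocol says only that ARBA will be estimated from the same mixed model; it gives no time formula.

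**The concern.** An annualized rate needs a numerator and a denominator that cover the same interval. Here the change includes whatever happened between the reference scan and first dose, and the time leaves that period out. The direction is known: T2 rates come out too high and ARBA too negative. The relative error is largest when follow-up is short and fades as it lengthens. In the cumulative T2 table, a constant lesion rate would therefore appear to fall from Month 0–3 to later intervals. In a single-arm study no control group would expose that pattern as an artefact. For the T2 model, the SAP also departs from the protocol's offset without giving a reason.

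**Working it through.** The documents contain no T2 rate, no ARBA value and no scan-to-dose gap, so there is no planned figure to reproduce. The check is of the formulas.

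**Inputs**
- Target days for Months 3, 6, 12, 24 and 60: 91, 182, 365, 730 and 1826 (SAP Part I 2.3.4, Table 2). The SAP's rule, the integer part of X × 365.25/12, returns these exactly.
- ARBA time: MRI date − first dose date + 1 (SAP Part I 8.2.4).
- Gap g, in days from reference scan to first dose: **assumed**, 7 to 90 days. The baseline definition implies only that g is at least 1.

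**Formula.** First dose is Day 1, so a scan on study day d lies d − 1 days after it. The SAP's time is (d − 1) + 1 = d. The true scan-to-scan interval is d − 1 + g. At a constant true rate:

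overstatement = (d − 1 + g)/d − 1 = (g − 1)/d

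With g = 1 the added day cancels the gap exactly and there is no bias. SAP 8.2.1 does not spell out the +1 for T2; I take the same convention as in 2.3.2 and 8.2.4. Without it the figures are slightly higher (g = 30, Month 3: 30/90 = 33.3% instead of 29/91 = 31.9%).

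**Overstatement by assumed gap**

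| g (days) | Month 3 | Month 6 | Month 12 | Month 24 | Month 60 |
|---|---|---|---|---|---|
| 7 | 6.6% | 3.3% | 1.6% | 0.8% | 0.3% |
| 14 | 14.3% | 7.1% | 3.6% | 1.8% | 0.7% |
| 30 | 31.9% | 15.9% | 7.9% | 4.0% | 1.6% |
| 45 | 48.4% | 24.2% | 12.1% | 6.0% | 2.4% |
| 90 | 97.8% | 48.9% | 24.4% | 12.2% | 4.9% |

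**Negative binomial offset.** Simulation with 20,000 patients, overdispersed counts, an intercept-only model, a true rate of 1.00 per year and g = 30. The first-dose offset gave 1.34, 1.14, 1.07 and 1.04 at Months 3, 6, 12 and 24. The scan-to-scan offset gave 1.01, 0.98, 0.99 and 1.00.

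**ARBA.** With true annual rate r, the SAP formula returns (1 + r)^((d − 1 + g)/d) − 1. For an assumed r = −0.50% per year and g = 30, Month 6 is 0.995^(211/182) − 1 = −0.58%. Months 3, 12, 24 and 60 give −0.66%, −0.54%, −0.52% and −0.508%.

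**Higher activity before first dose.** Suppose the T2 rate before dosing is twice the on-treatment rate (assumption) and g = 30. The SAP's rule overstates the on-treatment rate by (90 + 60)/91 − 1 = 64.8% at Month 3 and (364 + 60)/365 − 1 = 16.2% at Month 12. A scan-to-scan time leaves (90 + 60)/(90 + 30) − 1 = 25% and (364 + 60)/(364 + 30) − 1 = 7.6%. The correction then removes much of the bias, but not all of it.

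**The case against.** The best defence is that the SAP deliberately defines the T2 rate from first dose, and that counting from the reference scan brings untreated days into an on-treatment rate. It does not rescue the rule. A scan-to-scan count cannot be split at the dose date, so starting the clock at first dose leaves pre-dose lesions in the numerator and removes only their time.

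Other points stand and limit the finding.
- **Size.** A reader might take the percentages as estimates of the actual error. They are not: the gap appears nowhere in the documents, and at 7 days the Month 3 figure is only 6.6%.
- **Protocol authority.** A reader might infer that the SAP breaks the protocol for all the MRI rates. The protocol fixes the time only for the T2 model offset. It sets none for a crude T2 rate or for ARBA.
- **The table.** A reader might infer an artificial decline in atrophy from the same cumulative table. That table holds T2 rates only; ARBA is summarized by visit. Percent brain volume change that is not annualized is unaffected.
- **Relevance.** Under protocol Table 6-1 and 6.4.3, routine MRI in this study began at Visit 5 (Month 12), so Month 3 and 6 values must come largely from prior studies, whose schedules are not given here. The study's interest is long-term, where the effect is small. MRI is a secondary, descriptive endpoint and no decision rule depends on it.

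Against this, the gap need not be short for everyone. Only phase II/III patients entering under Amendment 8 were required to have an MRI at entry, and the protocol foresees gaps between studies (5.5.7, 6.1, 6.2). A comparator patient starting fingolimod here could have a reference scan from the prior study.

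**Conclusion.** The mismatch is in the text and should be corrected. For the T2 model offset the SAP departs from protocol 9.5.1.2. For the crude T2 rate and ARBA the case rests on consistency between change and time. The direction is certain whenever the reference scan precedes first dose by more than one day.

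The size is about (gap − 1)/days at a constant rate and depends wholly on an unstated gap. On the illustrative 14 to 45 days it matters at Months 3 to 12, is modest at Month 24 (2–6%) and is minor at Month 60 (0.7–2.4%). Even a 90-day gap gives under 5% at Month 60. The documents do not support a reading that the long-term MRI conclusions are materially wrong, or that every annualized rate is biased. They do support the narrower warning that a fall in the T2 rate across the early cumulative intervals could be partly artefact.

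**What to change.** In SAP Part I 8.2.1 and 8.2.4, define time as the date of the post-baseline scan minus the date of the reference scan actually used, including the end-of-core scan for switchers where that is the reference. Use it in three places: the crude T2 denominator, the negative binomial offset and the ARBA time (#days and k). Keep first dose for assigning visit windows. Report the distribution of the gap between reference scan and first dose, so that readers can see the actual size.

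The cost is a small derivation change. The reference-scan date is needed anyway to identify the last MRI before Day 1. The downside is that the interval then includes a short pre-dose period and lesions formed in it stay in the count, so some upward bias remains if activity was higher before treatment. State this as a limitation beside the table.

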8.2.2 Total volume of T2 lesions and T1 hypointense lesion

Total volume of T2 lesions and T1 hypointense lesion (black hole) volume will be summarized separately by presenting descriptive statistics for change from FDF baseline values by visit.

8.2.3 Percent brain volume change (PBVC)

Descriptive statistics on normalized brain volume at core baseline and percent brain volume change from FDF baseline will be presented by visit. Additionally, a mixed effects model with repeated measures will be used with visit, normalized brain volume at core baseline, T2 lesion volume at first dose of fingolimod baseline and Gd-T1 lesion count at first dose of fingolimod baseline as fixed effects and individual patient as a random effect. Kenward and Rogers' adjustment for the degrees of freedom will be applied. Based on this model, least square mean, standard error, and a two-sided 95% CI will be displayed for each group.

When an assessment is not provided by the reading center (i.e. 2399 results relative to FDF), derivation rules regarding percent brain volume change from FDF baseline should be followed as below:

- Patients who were randomized to fingolimod in core: PBVC relative to FDF baseline = PBVC relative to FDD.
- Patients who were randomized to a treatment (placebo or interferon) other than fingolimod in core and switched to fingolimod in extension:
 - If the record of extension FDD was available in the extension database, PBVC relative to FDF baseline = PBVC relative to extension FDD.

- If no records relative to FDF baseline were available in the extension, the formula stated below was used to get the PBVC relative to FDF baseline:

$$p2=100*[(p3-p1)/(p1+100)].$$

where p1=PBVC relative to FDD at end of core, p2=PBVC relative to FDF, p3=PBVC relative to FDD, and $p3 = [(1+p1/100)*(1+p2/100)-1]*100$.

8.2.4 Annualized rate of brain volume change (ARBA)

The annualized rate of brain volume change is an “averaged annual percentage change” in brain volume. The logic of interest rates applies. The formula for ARBA is as below:

$$ARBA = [(SIENA/100+1) ^ (365.25/\#days)-1]*100$$

$$SIENA=(Vk/V0-1)*100$$

$$k=days/365.25$$

where V0 is the brain volume at time 0, and Vk is the brain volume at time k (where k is the time in years).

The annualized rate of brain volume change relative to FDF baseline will be calculated from the SIENA estimate of the percentage brain volume change relative to FDF baseline and the number of days in study relative to FDF. For the calculation of k and V0, below rules should be followed:

- Patients who were randomized to fingolimod: k = MRI date – first dose date +1; V0 = brain volume at FDD
- Patients who were randomized to a treatment (placebo or interferon) other than fingolimod in core and switched to fingolimod in extension control treatment: k = MRI date – first dose date of extension +1; V0 = brain volume at extension FDD (if there is record), or at the end of core (if there is no record at extension FDD) .

Descriptive statistics on ARBA will be presented by visit. Additionally, a mixed effects model with repeated measures will be used with visit, normalized brain volume at core baseline, T2 lesion volume at first dose of fingolimod baseline and Gd-T1 lesion count at first dose of fingolimod baseline as fixed effects and individual patient as a random effect. Kenward and Rogers’ adjustment for the degrees of freedom will be applied. Based on this model, least square mean, standard error, and a two-sided 95% CI will be displayed for each group.

8.3 Analysis of EDSS scores

The EDSS scores are used for the confirmation of MS relapse and the confirmation of disability progression. All EDSS summaries are based on the fingolimod full analysis set.

